APPENDIX 3. The Oswestry Disability Index Questionnaire

Last Name: _____
First Name: _____
DOB: _____

Oswestry Disability Questionnaire

This questionnaire has been designed to give us information as to how your back or leg pain is affecting your ability to manage in everyday life. Please answer every section and mark in each section only the ONE box which applies to you. We realize you may consider that two of the statements in any one section relate to you, but please just mark the box which most closely describes your problem.

Section 1 – Pain Intensity

- I have no pain at the moment.
- The pain is very mild at the moment.
- The pain is moderate at the moment.
- The pain is fairly severe at the moment.
- The pain is very severe at the moment.
- The pain is the worst imaginable at the moment.

Section 2 – Personal Care (washing, dressing, etc.)

- I can look after myself normally but it is very painful.
- I can look after myself normally but it is very painful.
- It is painful to look after myself and I am slow and careful.
- I need some help but manage most of my personal care.
- I need help every day in most aspects of my personal care.
- I need help every day in most aspects of self-care.
- I do not get dressed, wash with difficulty, and stay in bed.

Section 3 - Lifting

- I can lift heavy weights without extra pain.
- I can lift heavy weights but it gives extra pain.
- Pain prevents me from lifting heavy weights off the floor, but I can manage if they are conveniently positioned (i.e. on a table).
- Pain prevents me from lifting heavy weights, but I can manage light to medium weights if they are conveniently positioned.
- I can lift only very light weights.
- I cannot lift or carry anything at all.

Section 4 – Walking

- Pain does not prevent me walking any distance.
- Pain prevents me walking more than 1 mile.
- Pain prevents me walking more than ¼ of a mile.
- Pain prevents me walking more than 100 yards.
- I can only walk using a stick or crutches.
- I am in bed most of the time and have to crawl to the toilet.

Section 5 – Sitting

- I can sit in any chair as long as I like.
- I can sit in my favorite chair as long as I like.
- Pain prevents me from sitting for more than 1 hour.
- Pain prevents me from sitting for more than ½ hour.
- Pain prevents me from sitting for more than 10 minutes.
- Pain prevents me from sitting at all.

Section 6 – Standing

- I can stand as long as I want without extra pain.
- I can stand as long as I want but it gives me extra pain.
- Pain prevents me from standing more than 1 hour.
- Pain prevents me from standing for more than ½ an hour.
- Pain prevents me from standing for more than 10 minutes.
- Pain prevents me from standing at all.

Section 7 – Sleeping

- My sleep is never disturbed by pain.
- My sleep is occasionally disturbed by pain.
- Because of pain, I have less than 6 hours sleep.
- Because of pain, I have less than 4 hours sleep.
- Because of pain, I have less than 2 hours sleep.
- Pain prevents me from sleeping at all.

Section 8 – Sex life (if applicable)

- My sex life is normal and causes no extra pain.
- My sex life is normal but causes some extra pain.
- My sex life is nearly normal but is very painful.
- My sex life is severely restricted by pain.
- My sex life is nearly absent because of pain.
- Pain prevents any sex life at all.

Section 9 – Social Life

- My social life is normal and cause me no extra pain.
- My social life is normal but increases the degree of pain.
- Pain has no significant effect on my social life apart from limiting my more energetic interests, i.e. sports.
- Pain has restricted my social life and I do not go out as often.
- Pain has restricted social life to my home.
- I have no social life because of pain.

Section 10 – Traveling

- I can travel anywhere without pain.
- I can travel anywhere but it gives extra pain.
- Pain is bad but I manage journeys of over two hours.
- Pain restricts me to short necessary journeys under 30 minutes.
- Pain prevents me from traveling except to receive treatment

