Patients who are deemed eligible to participate in the study and are willing to participate will be asked by a trained study physician assistant (PA) to complete the research informed consent. This document will be summarized verbally by the PA and potential participants will be given the opportunity to ask questions about the protocol or their involvement prior to providing consent. Those who agree to

participate and provide research informed consent will be enrolled in the study, and given a copy of the research informed consent document. The patient's informed consent would be added to the patient's chart.

A computer generated randomization scheme will be employed and the randomization outcomes will be sealed in envelopes. On the day of surgery, in the operating room, the circulating nurse will pick an envelope from the randomized stack, unseal the envelope, and based on the outcome (even or odd), assign the patient to one of the two bone graft groups. While the study intervention group (even) will receive 5cc Vivigen and local autograft, the control group (odd) will receive small kit rhBMP-2 with local autograft. Anesthesiologists will use their usual pre-operative and intra-operative techniques for all study participants.

The surgical team, including the surgeons, will be blinded to the treatment options until decompression/instrumentation have been completed. The patients and all staff, including hospital nursing staff, case management, and physical therapists, will be blinded as to which bone graft treatment the patient received.

The primary outcome in this study will be the mean Oswestry Disability Index (ODI) score. The ODI is one of the most commonly utilized condition-specific measures of disability used in the management of spinal disorders [9]. The ODI Version 2.0 is what the Virtua Memorial Spine Center currently uses to examine patient disability preoperatively, as well as two weeks, 6 weeks, 3 months, 6 months, and 1 year postoperatively. The ODI has 10 sections of six statements with the first statement corresponding to a score of 0 indicating no disability and the last statement corresponding to a score of 5 indicating maximum possible disability. The final score which is calculated as: $[\text{total score}/(5 \times \text{number of questions answered})] \times 100\%$, could range from 0% to 100% [9].

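### Does the Oswestry form in Appendix 3 make the primary outcome impossible to score?

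*Combined protocol and SAP*

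**What the plan says.** Study Methodology makes the ODI the primary outcome: "The primary outcome in this study will be the mean Oswestry Disability Index (ODI) score". It names the version and says that it is already in use: "The ODI Version 2.0 is what the Virtua Memorial Spine Center currently uses to examine patient disability preoperatively". It then gives the structure, "The ODI has 10 sections of six statements with the first statement corresponding to a score of 0 indicating no disability", and the upper anchor, "the last statement corresponding to a score of 5 indicating maximum possible disability". The final score is the total divided by five times the number of questions answered, times 100, and it "could range from 0% to 100" per cent.

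Appendix 3 holds the questionnaire. As the text reads, eight of its ten sections have six statements. Section 2 (personal care) has seven: the first two are both "I can look after myself normally but it is very painful", and the sixth, "I need help every day in most aspects of self-care", nearly repeats the fifth. Section 10 (traveling) has five. Its third statement concerns journeys of more than two hours and its fourth is "Pain restricts me to short necessary journeys under 30 minutes". Its fifth is the last line of the whole text.

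**The concern.** Set beside the scoring description, the appendix seems to contradict it. Section 2 has one statement too many, its first two boxes cannot be told apart, and none describes self-care without pain, although the first box is meant to signify no disability. Section 10 has one statement too few and a gap in the middle of its range.

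If boxes were coded in order from 0, Section 2 would run to 6 and Section 10 only to 4, while the formula allows 5 for each. A recovered patient would have no fitting answer in Section 2, and two patients giving the same answer could score differently. As this is the primary instrument, the validity of the trial's main result would be in question.

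**Working it through.** **1. Could the faults belong to the reading of the PDF?** Statements per section, in order: 6, 7, 6, 6, 6, 6, 6, 6, 6, 5. The irregularities are one line repeated word for word, one pair of near-duplicates and one short list. A repeated line that displaced the true first statement would account for the top of Section 2. A dropped line would account for the jump in Section 10, which is also where the text stops, on the only statement in the appendix without a closing full stop. These are familiar results of machine reading. The body of the protocol describes six statements in every section of a version in routine use.

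**2. Does the formula fail?** It needs a score from 0 to 5 for each answered section and the number answered. Study Methodology fixes both ends of the scale.

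- Stated rule (first = 0, last = 5): the maximum is 10 × 5 = 50, and 50/50 × 100 = 100%. With nine sections answered it is 45/45 × 100 = 100%. The minimum is 0%.
- Coding by position, which the protocol does not state: the full-form maximum is 8 × 5 + 6 + 4 = 50, again 100%. Only if Section 10 alone is skipped does it become 46/45 = 102.2%, and if Section 2 alone is skipped 44/45 = 97.8%.

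The out-of-range values therefore come from a coding rule that conflicts with the stated upper anchor. Under the stated rule, the most that could be undefined is the value of the intermediate boxes in two sections.

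**3. How much could that matter if the printed form were really faulty?** Inputs from the sample-size paragraph: SD 10, difference 8, power 80%, significance level 0.05, 26 per group required and 30 enrolled.

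- The plan's own figure: standardized difference 8/10 = 0.8. A two-sided two-sample t test needs 25.52, rounded up to 26, as stated. Power is 80.7% at 26 and 86.1% at 30 per group. The two-sided test is used here because it reproduces 26.
- One raw step in one section: 1/(5 × 10) × 100 = 2 ODI points for that patient, or 1/45 × 100 = 2.2 with nine sections answered.
- An even choice between identical boxes scored 0 and 1 has mean 0.5 and SD 0.5 raw points, which is 1 ODI point each. The mean shift cancels between arms where the same share of patients faces that choice. Even in the extreme case of all patients in one arm and none in the other, it would be 1 point against 8.
- Independent scoring error with SD *e* raises the SD to √(100 + *e*²). The values of *e* are assumptions:

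| *e* | Total SD | Power, 26 per group | Power, 30 per group |
|---|---|---|---|
| 0 | 10.00 | 80.7% | 86.1% |
| 1 | 10.05 | 80.4% | 85.8% |
| 2 | 10.20 | 79.2% | 84.8% |
| 4 | 10.77 | 74.7% | 80.8% |

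The twin boxes correspond to *e* = 1. Even at *e* = 4, the 30 per group to be enrolled keep power above 80% if all are analyzed.

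**The case for a change.** The strongest reply is that a reading fault does not explain everything easily. Deleting the repeated line leaves six statements in Section 2, but the first still describes very painful self-care. The near-duplicates differ in wording, so they are not a plain line repeat. The gap in Section 10 lies mid-list, so text cut off at the end does not produce it, and its last line reads like a natural endpoint. The other eight sections came through with six statements each. The form is used before surgery and at five visits afterwards, so 60 patients yield up to 60 × 6 = 360 forms.

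The counts stand, and so does the point that simple truncation does not explain Section 10. But a displaced line and a dropped line explain the main irregularities, and the documents cannot show that the form given to patients carries any of them.

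The harm also shrinks on inspection. The form's instructions ask for the closest box, so a recovered patient who marks the first box in Section 2 scores 0 under the stated rule. A section left blank is handled by the denominator. The same form serves both arms, and no between-arm bias has been shown.

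**Conclusion.** The concern does not hold. The irregularities in Appendix 3 are of a kind that machine reading of a PDF produces, and the documents give no ground for attributing them to the form in use. The protocol names the version, describes six statements per section and anchors each section at 0 and 5, so the primary outcome can be scored by the stated formula.

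This rests on two assumptions: that the center uses Version 2.0, as the protocol says, and that scoring follows the stated anchors and not box position. If the printed form did carry the faults, the cost would be about 2 points per ambiguous step for an individual patient and, with 1 point of added SD, a power loss of 0.3 percentage points at 26 per group. Putting the correct Version 2.0 form in its place would only restore what Study Methodology already specifies. Discarding the two sections would be worse than the ambiguity: it would remove 2 of 10 items, a fifth of the instrument, including answers already given, and the denominator is there for unanswered questions. Comparing the appendix with the original file is reasonable housekeeping, but nothing in the design, analysis or conclusions depends on it.
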